8.1 Study design

8.1.1 Type of study

This is a 12-month, multi-centre, prospective, non-interventional study assessing the safety and effectiveness of Tresiba[®] 100 units/mL or Tresiba[®] 200 units/mL OD, used with any anti-diabetic treatment according to local label, in T1DM or T2DM patients who use insulin where the physician has decided to start the patient on Tresiba[®] treatment.

The study is non-interventional as the patients are treated according to routine clinical practice and the local label upon the treating physician's decision. This is under the category of PASS. The location of study information within this protocol is available in ENCePP checklist for study protocols (Annex 2).

The study is expected to be conducted within the following countries: Denmark, Germany, The Netherlands, Spain, Sweden, Switzerland, Italy, and the United Kingdom (UK).

Novo Nordisk ceased the distribution of Tresiba[®] in Germany at the end of September 2015. Germany will be removed from this study, thus patients enrolled in Germany based on the protocol version 2.0 will be discontinued. Data obtainable up to the discontinuation date will be included in the analyses, as appropriate and specified in the SAP.

[figure not shown]
Anonymised patient level data will be collected by the patients' physicians and an eCRF will be used to capture the data.

The total study duration for the individual patients will be a maximum of 63 weeks (baseline: 4 weeks, observation period: up to 52 weeks +/-45 days).

Throughout the study, change in dosage, dose interval and add-on or removal of bolus insulin, other oral anti-diabetic drugs and/or glucagon-like peptide-1 agonists is expected and will not exclude the patients to participate in the study and in the primary and secondary endpoint analyses.

Patients with T1DM and T2DM who are treated with insulin will be followed for 4-weeks before (baseline period), and a maximum of 12 months after switching to Tresiba[®] (observation period). During the 4-week baseline period, physicians who plan to start Tresiba[®] treatment begin evaluating the patient's glycaemic control and confirm the decision to switch treatment. As specified in the SmPC, close glucose monitoring is recommended during the transfer from other insulin medicinal products and in the following weeks (2) and allows individualised treatment to be provided. During the 4-week baseline period patients will continue on their current therapy, including any diet and exercise recommendations. This baseline period will provide a portrait of the patient's risk of developing hypoglycaemia. Each patient acts as his/her own reference where the baseline period allows assessment of hypoglycaemic episode rates on current insulin and thus enables comparisons with the hypoglycaemic episode rates after switching to Tresiba[®]. In clinical practice, possible outcomes during and after the 4-week baseline period are presented in [Figure 8-1](#) below.

[figure not shown]
Figure 8–1 Flowchart of patient disposition during and after the 4-week baseline period

At the end of the baseline period, patients eligible for the study who continue to qualify for Tresiba® treatment (according to the treating physician) will initiate Tresiba® treatment (visit 2). Prospective hypoglycaemic episode data will be collected at the following time points during Tresiba® treatment: 0 months (+14 days, visit 2), 3 months (± 45 days, visit 3), 6 months (± 45 days, visit 4), 9 months (± 45 days, visit 5) and finally at 12 months (± 45 days, visit 6). Visits are not protocol defined and will be conducted as part of routine clinical monitoring of patients. Key study observational endpoints are outlined above in Section [7.3](#).

The study design is summarised schematically in [Figure 8–2](#).

Figure 8–2 Schematic of study design

Abbreviations: OD=once daily; V=visit.

Grey arrows indicate 4-week periods when hypoglycaemic episodes will be recorded prospectively in patient diaries. At visit 1 patients will be asked to recall any severe hypoglycaemic episodes over the previous 6 months. Visits are defined as contact with health care provider (physician or nurse).

8.1.2 Rationale for study design

The non-interventional study design reflects clinical practice in a way that a randomised controlled study cannot, as it allows for the inclusion of patients and the treatment to be solely at the discretion of the treating physician.

The study design is a non-interventional study with a 4-week baseline reporting period. The 4-week baseline period provides an opportunity to collect a portrait of the patient's risk of developing hypoglycaemia. Each patient acts as his/her own reference where the baseline period allows assessment of hypoglycaemic rates on current insulin and thus, enables comparisons with the hypoglycaemic rates after switching to Tresiba®.

In the clinical development programme Tresiba® has consistently demonstrated similar efficacy to other insulin analogues in the treat-to-target trial designs, but a more favourable safety profile with fewer hypoglycaemic episodes. Thus the primary observational endpoint, change from the baseline period (4-week baseline period) in the number of any hypoglycaemic episodes occurring during the 12-month observation period with Tresiba® is relevant to assess in a real world setting.

The secondary effectiveness endpoint, HbA1c, is the most widely accepted measure of overall, long-term blood glucose control in patients with diabetes (7). In addition, it is a laboratory parameter and consequently the probability of assessment bias is limited. Other measures could have non-ignorable measurement errors, however these are not pivotal observational endpoints, and regardless, it is not possible to alleviate assessment bias in a similar way.

The study is based on prospectively collected clinical data and PROs as part of normal clinical practice. The prospective non-interventional study design in a large-scale setting with a sufficient number of patients, and thus an adequately powered study, is needed to analyse the safety and effectiveness of Tresiba[®] with regard to the primary and secondary endpoints in a real-world population of T1DM and T2DM patients.

In order to minimise potential reporting and prescribing bias and to ensure face validity of the study, data will be collected from patients that the physician plans to switch to Tresiba[®] over a similar time frame (approximately 6 months) within each country.

The 12-month observation period is expected to be sufficient to initiate and optimise the study treatment regimen and to obtain long-term real world data for safety and effectiveness evaluation.

8.1.3 Treatment of patients

Patients with T1DM as well as patients with T2DM requiring insulin therapy will be treated according to routine clinical practice at the discretion of the treating physician. The assignment of the patient to Tresiba[®] is not decided in advance by the protocol but falls within routine practice.

The initiation of Tresiba[®] is at the discretion of the treating physician. All anti-diabetic treatment will be prescribed and used in accordance with local label, including the study product Tresiba[®], marketed as Tresiba[®] (100 units/mL / 200 units/mL) in a prefilled pen injector (FlexTouch[®]).

Tresiba[®] will be prescribed by the physician under routine clinical practice conditions (see Section 8.1.5). The physician will determine the starting dose, based on local label, as well as later changes to dose, if any. Patients will be instructed as per usual practice to use Tresiba[®] as specified in local package insert (ie, OD subcutaneous [SC] administration at any time of the day, preferably at the same time every day). Any other anti-diabetic treatments can be changed or doses adjusted at the discretion of the treating physician.

Diet and exercise counselling may be conducted as per the standard of care at the investigational site.

All other prescription and non-prescription drugs may be used.

8.1.4 Rationale for treatment

Patients with T1DM or T2DM (insulin users) are eligible for treatment with Tresiba[®] in accordance with the approved SmPC.

8.1.5 Study supplies

Study product:

The study product is IDeg, marketed as Tresiba[®] (100 units/mL / 200 units/mL) in a prefilled pen injector (FlexTouch[®]) for SC injection.

Packaging and labelling of study product:

Tresiba[®] will be prescribed by the physician under normal clinical practice and will be obtained/purchased from the pharmacy based on the physician's prescription and according to local regulations.

8.2 Setting

A broad population of patients with T1DM or insulin using patients with T2DM is eligible for this study. The purpose of this study is to monitor the safety and effectiveness of Tresiba[®] in a general real world diabetic population. The decision to initiate treatment is entirely the treating physician's, as is the treatment regimen and adjustment of the treatment.

Patients who meet the eligibility criteria, outlined in Section [8.2.2](#), will be eligible regardless of sex, race or ethnicity. Both general practitioners (GPs)/specialists and hospital sites will be included. The study will include multiple geographical sites to potentially enhance generalisability and ensure sufficient numbers of patients with T1DM or T2DM who use insulin are included for adequately powered analysis of the primary and secondary endpoints. Inclusion and exclusion criteria applied in this study should ensure comparability of study results for a general broad population of patients with T1DM or T2DM.

In order to facilitate identification of suitable sites by the Contract Research Organisation (CRO), Novo Nordisk will, where possible and relevant, supply the CRO, [REDACTED], with information on local primary care formulary status for Tresiba[®] and information about local primary care prescription density by geographical area. Both GPs/specialists and hospital sites will be included.

8.2.1 Number of patients to be studied

Patients with T1DM or T2DM, eligible for this study will be included. All data collected will be included in the analysis.

Planned number of patients to be included: 1216 patients are expected to switch treatment to Tresiba[®] following the 4-week baseline period, including the patients from sites in Germany, according to the SAP.

Planned number of patients to complete the study in the participating countries: in total, 1034 are planned to complete the study (based on a withdrawal rate of 15%).

8.2.2 Inclusion criteria

Patients must meet the following inclusion criteria to be eligible for the study.

1. Informed consent obtained before any study-related activities (Study-related activities are any procedure related to recording of data according to the protocol)
2. Male or female patients ≥ 18 years of age at time of informed consent
3. T1DM (diagnosed clinically) prior to inclusion in the study, and/or T2DM, insulin using patients (diagnosed clinically) prior to inclusion in the study
4. Planned initiation with Tresiba[®]

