7.1 Primary objective

The primary objective is to monitor and assess the safety of Tresiba[®], used with any other anti-diabetic treatment and according to label, by analysing whether treatment with Tresiba[®] OD is associated with a change in the rate of any hypoglycaemic episodes occurring during the

observation period, compared to the rate of any hypoglycaemic episodes occurring during the baseline period, where the patient continues the prior basal insulin as part of their anti-diabetic treatment regimen. The prior basal insulin can be any type of basal insulin.

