8.2.3 Exclusion criteria

Patients presenting with any of the following will not be eligible to participate in the study:

1. Known or suspected hypersensitivity to Tresiba[®] or any of the excipients listed in Section 6.1 of the SmPC or related products
2. Previous participation in this study (ie, provision of informed consent)
3. Patients who have previously been treated with Tresiba[®]
4. Mental incapacity, unwillingness or language barriers precluding adequate understanding or cooperation

Patients who are non-compliant with any of the inclusion/exclusion criteria, but included in the study, must be excluded immediately.

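### The objectives compare Tresiba with a prior basal insulin, but no eligibility or analysis-set rule requires one, so a T2DM patient on mealtime insulin only can enter the primary estimate

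*Protocol*

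**What the plan says.** **Objectives.** Section 7.1 sets Tresiba against a baseline period "where the patient continues the prior basal insulin as part of their anti-diabetic treatment regimen" and adds that this may be any type of basal insulin. Section 7.2, the abstract (Section 3.3) and the study information table define the comparator in the same way.

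**Eligibility.** Criterion 3 in Section 8.2.2 reads "T1DM (diagnosed clinically) prior to inclusion in the study, and/or T2DM, insulin using patients (diagnosed clinically) prior to inclusion in the study". Criterion 4 is "Planned initiation with Tresiba", which is an initiation and not a switch from a basal product. The only exclusion in Section 8.2.3 that concerns earlier treatment is "Patients who have previously been treated with Tresiba".

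**Design text.** Section 8.1.1 says that "the baseline period allows assessment of hypoglycaemic episode rates on current insulin and thus enables comparisons with the hypoglycaemic episode rates after switching to Tresiba". Current insulin is a wider comparator than prior basal insulin.

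**Analysis.** Section 8.2.1 says that all collected data enter the analysis. Section 8.7.1 defines the full analysis set (FAS) as everyone with at least one Tresiba dose at visit 2, and Sections 8.7.2 and 8.7.2.1 run the primary analysis on it, separately for T1DM and T2DM.

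**Data available.** Table 8-1 records anti-diabetic treatment type and dose, with the insulin regimen, from visit 1 onwards.

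**The concern.** Each patient is his or her own control and there is no comparator group, so the meaning of the primary result depends on what the patient was taking during the four baseline weeks. The objectives presuppose a basal insulin in those weeks. The criteria that a site applies do not.

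Take a T2DM patient on mealtime insulin only. This patient meets all four inclusion criteria, is caught by no exclusion, and is in the FAS after one dose at visit 2. His or her baseline diary is not a rate on a prior basal insulin, and the change from it mixes the product with the addition of a basal component.

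A pooled estimate containing such patients answers a different question from the one in Section 7.1. The planned effect is small against its SD (1 against 7 episodes per patient-year), so a minority with a different mean change could matter. Because T1DM and T2DM are analysed separately, such T2DM patients would not be diluted by the T1DM group.

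**Working it through.** **1. Sections side by side**

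| Section | Requirement on prior insulin |
|---|---|
| 7.1, 7.2 (objectives) | A prior basal insulin, of any type |
| 8.1.1 (design) | Treated with insulin; comparator is current insulin |
| 8.2.2 (inclusion) | T1DM: diagnosis. T2DM: insulin using. Basal not named |
| 8.2.3 (exclusion) | No earlier Tresiba; absence of basal insulin not listed |
| 8.2.1, 8.7.1 (analysis) | Everyone dosed at visit 2 |

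No section makes a prior basal insulin a condition of entry or of analysis.

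**2. The plan's own sample size (Section 8.5)**

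Inputs: mean paired difference 1 episode per patient-year, SD 7, two-sided alpha 0.05 (Section 8.7.2.2), power 90%.

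- Normal approximation: n = [7 × (1.960 + 1.282) / 1]² = 514.9, so 515.
- Exact paired t-test (noncentral t): n = 517, power 0.9001. This matches the stated 517.
- Withdrawal: 517 / 0.85 = 608.2, against the stated 608.

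The sample size is right on its own inputs.

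**3. Illustration of dilution**

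Let f be the share with no prior basal insulin and c their mean reduction (negative if their rate rises). The protocol gives neither, so both are assumptions. The other patients fall by 1 per patient-year, and the within-group SD is 7.

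- Pooled mean reduction: m = (1 − f) × 1 + f × c
- Pooled SD: s = √[49 + f(1 − f)(1 − c)²]
- Power: noncentral t, n = 517, noncentrality m√517 / s

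Example, f = 5% and c = 0: m = 0.95; s = √(49 + 0.0475) = 7.003; noncentrality 0.95 × 22.738 / 7.003 = 3.084; power 86.8%.

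| f | No change (c = 0) | Rate rises by 1 (c = −1) | Rate rises by 5 (c = −5) |
|---|---|---|---|
| 2% | m 0.98, power 88.8% | m 0.96, power 87.5% | m 0.88, power 80.9% |
| 5% | m 0.95, power 86.8% | m 0.90, power 83.0% | m 0.70, power 60.7% |
| 10% | m 0.90, power 83.0% | m 0.80, power 73.4% | m 0.40, power 24.1% |
| 20% | m 0.80, power 73.6% | m 0.60, power 48.9% | m −0.20 (sign reversed) |

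These figures use the planning model of Section 8.5, not the regression model of Section 8.7.2.1.

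**4. Price of restricting the primary comparison**

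If 5% are set aside, 517 × 0.95 = 491 completers remain. With the undiluted mean of 1 and SD 7, the noncentrality is √491 / 7 = 3.166 and power is 88.5%. On the same assumption, keeping them in with no change gives 86.8%.

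**The case against.** **The protocol describes a switch throughout.** Sections 3.4, 8.1.1, 8.2.1 and 8.5 all speak of switching, and the objectives name a prior basal insulin. A site reads the whole protocol and may enrol only basal users. This stands as evidence of intent, and nothing shows that a patient without basal insulin was enrolled. But intent is not a criterion that a site checks or a rule that an analyst applies.

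**Other example patients are weaker.** A reader might infer that a newly diagnosed, untreated T1DM patient also qualifies, since criterion 3 asks only for the diagnosis. The design text points the other way: "Patients with T1DM and T2DM who are treated with insulin will be followed for 4-weeks before (baseline period". Footnote 1 to Table 8-1 also calls for a physician statement that four weeks on the current medication is not a safety problem. A reader might likewise count pump users as lacking basal insulin. The protocol does not classify pumps, and having no separate basal product is not the same as having no basal insulin. Only T2DM on mealtime insulin alone is a clear gap.

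**The study makes no causal claim.** Section 8.9 says that no causal conclusion can be drawn and describes exploring associations with other anti-diabetic regimens. Section 8.1.1 expects other diabetes drugs to be added or removed and keeps those patients in. This lowers the stakes. It does not settle which comparator the primary estimate has, because Section 7.1 still names a prior basal insulin. Changes in other drugs after visit 2 also differ from having no basal insulin at baseline.

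**Breadth is deliberate.** Sections 8.2 and 8.2.5 want a broad population. That is a fair reason to widen the comparator, but the objectives have not been widened.

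**Conclusion.** The objectives require a prior basal insulin, and the eligibility criteria and FAS do not. A T2DM patient on mealtime insulin only can enter and be counted in the primary estimate. That is an internal mismatch in what this protocol fixes. A later restriction of the analysis would have to depart from Sections 8.2.1 and 8.7.1, while analysing as written departs from Section 7.1.

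The size cannot be determined from the document. Under an assumed 5% share with no change, power falls from 90% to about 87%; at 2% it is 88.8%. The large losses in the table need a sizeable share together with a rise of several episodes per patient-year, and nothing in the protocol points to that combination.

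A reader might infer that the primary result is already distorted, or that a true benefit will be hidden because adding basal insulin raises hypoglycaemia. The documents support neither. They give no count of such patients, no figure for the effect of adding a basal insulin, and no claim to isolate a causal difference between basal insulins. The point is moderate and does not invalidate the study.

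**What to change.** Reconcile Sections 7.1, 8.1.1, 8.2.2 and 8.7.1.

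- **Eligibility.** Amend criterion 3 so that both T1DM and T2DM patients are on a regimen containing basal insulin at visit 1, and state how premix and pump regimens are classified. Use the same comparator wording in Section 8.1.1.
- **Patients already enrolled.** Use the visit 1 treatment record (Table 8-1) to base the primary comparison on those with a prior basal insulin. Report the others separately as patients in whom a basal insulin was added, and give the full FAS result as a sensitivity analysis. Adjust Sections 8.2.1 and 8.7.1 to allow this.
- **Report the number** without prior basal insulin by diabetes type, so that the reader can judge whether the point matters.

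The cost is one eligibility line and one analysis rule on data already collected. A few patients leave the primary comparison and the population becomes slightly narrower than all insulin users. If the sponsor prefers to keep the full breadth, the alternative is to widen the comparator in Sections 7.1 and 7.2 to the prior insulin regimen. That removes the contradiction, but the primary result then no longer speaks only to replacing a basal insulin.

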8.2.3 Exclusion criteria

Patients presenting with any of the following will not be eligible to participate in the study:

1. Known or suspected hypersensitivity to Tresiba[®] or any of the excipients listed in Section 6.1 of the SmPC or related products
2. Previous participation in this study (ie, provision of informed consent)
3. Patients who have previously been treated with Tresiba[®]
4. Mental incapacity, unwillingness or language barriers precluding adequate understanding or cooperation

Patients who are non-compliant with any of the inclusion/exclusion criteria, but included in the study, must be excluded immediately.

8.2.4 Withdrawal criteria

The patient may withdraw at will at any time, for any reason. Patients may also be withdrawn early because of pregnancy or intention to become pregnant.

Management of subjects who are withdrawn

The treating physician as part of normal clinical practice should follow-up with the patients who have been withdrawn regarding any unresolved SADRs, MESI and pregnancies, as well as severe hypoglycaemic episodes (regardless of physician's evaluation of seriousness and causality).

The physician should inquire about the reason for discontinuation.

The reason for discontinuation should be recorded in the eCRF. A discontinuation occurs when a patient who has provided informed consent ceases participation in the study, regardless of the circumstances, prior to collection of data on visit 6.

If the patient withdraws from the study, and also withdraws consent for disclosure of future information, no additional data should be collected. The sponsor may retain and continue to use any data collected before such withdrawal of consent.

Patients who have been withdrawn from the study cannot be re-included in the study if they have already started Tresiba[®] treatment. The patient number must not be reused.

8.2.5 Rationale for eligibility criteria

The inclusion criteria are broad reflecting the real world population of T1DM and T2DM patients, i.e., patients treated under conditions of routine care, eligible for Tresiba[®] treatment.

Informed consent will only be valid for patients ≥ 18 years of age. The questionnaires are not designed for paediatric populations.

Patients with mental incapacity, unwillingness or language barriers precluding adequate understanding or cooperation are excluded to ensure the collection of robust and reliable data.

8.2.6 Flowchart

All visits and data collections are outlined below in [Table 8–1](#).

Table 8–1 Flow chart of study-related data collection

Study NN1250-4189	Planning to initiate	Initiation	Observation period			
			V3 ¹	V4 ¹	V5 ¹	V6 ¹
Visit Number (V)	V1 ¹	V2 ¹	V3 ¹	V4 ¹	V5 ¹	V6 ¹
Time of visit (Months)	-1	0	3	6	9	12
Visit window (days)		+14	±45	±45	±45	±45
PATIENT RELATED INFO/ASSESSMENTS						
Informed consent	X					
In/Exclusion criteria	X	X				
Initiation		X				
Withdrawal criteria		X	X	X	X	X
Demographic data	X					
Height, systolic and diastolic blood pressure (if available)	X					
Body weight (if available)	X	X	X	X	X	X
Diagnosis of diabetes	X					
Insulin use – is the patient a high dose insulin user (>80 U/day)	X					
Hypoglycaemia risk: is the patient prone to hypoglycaemia	X					
Concomitant ill/ medical history	X					
Anti-diabetic treatment type and dose ²	X	X	X	X	X	X
Concomitant medications	X	X	X	X	X	X
Reason for switching or not switching to Tresiba [®]		X				
First date on study insulin (Tresiba [®])		X				

Study NN1250-4189	Planning to initiate	Initiation	Observation period			
SAFETY AND EFFECTIVENESS						
Distribution and collection of patient diaries ³	X	X	X	X	X	X
Most recent FPG and date of measurement (if available)	X	X	X	X	X	X
Most recent HbA _{1c} and date of measurement (if available)	X	X	X	X	X	X
Total daily dose of bolus insulin on day prior to visit (if applicable)		X	X	X	X	X
Changes in any social, leisure and working activities due to insulin treatment		X	X	X	X	X
SADRs, MESI and pregnancies ⁴		X	X	X	X	X
Hypoglycaemic episodes ⁵	X	X	X	X	X	X
PRO questionnaires ⁶ : SF-36 (version 2) DTSQ ⁷	X	X	X	X	X	X
Patient preference			X	X	X	X
End of study						X ⁸

Abbreviations: DTSQ=diabetes treatment satisfaction questionnaire; FPG=fasting plasma glucose; HbA_{1c}=glycated haemoglobin A1c; MESI=medical events of special interest; SADR=serious adverse drug reaction; PRO=patient reported outcomes; SF-36=Short form-36; V=visit.

¹ Decision to initiate the study will take place 4 weeks prior to actual initiation of Tresiba[®] treatment, and with this a statement reported by the physician that use of current medication (for 4 weeks) will not be a safety problem for the patient. Patient material will be handed out at visit 1 to explain the importance of the baseline reporting period. It is not guaranteed that all patients will attend all visits.

² For anti-diabetic treatment also collect the insulin dosing regimen.

³ Patient diaries will include sections for recording information such as details of hypoglycaemia, insulin dosage, dose-time flexibility, and health economics resource use.

⁴ Each SADR will be spontaneously reported and recorded on a separate AE and safety information form according to existing reporting procedures. MESI includes medication errors.

⁵ Four weeks prospective hypoglycaemia assessment leading up to visits at Months 0, 3, 6, 9, and 12, in addition to a 6 month severe hypoglycaemia recall at visit 1.

⁶ Patients will be encouraged to fill the PRO questionnaires, preferably before any other study related procedures.

⁷ Status version of DSTQ at visits 1, 2, 3, 4, 5 and 6, change version of DSTQ at visit 6.

⁸ Preference of FlexTouch[®] over previous injection method.

